5.4.3 Supportive Secondary Virology Endpoints

5.4.3.1 Change from Baseline in Amount of SARS-CoV-2 Virus RNA as Measured by RT-qPCR at Each Timepoint

The change from baseline in amount of SARS-CoV 2-virus RNA as measured by RT-qPCR will be analyzed at Day 3, Day 5, Day 7 and Day 14 separately. The statistical method is detailed in Section 5.1.

5.4.3.2 Proportion of Patients Positive for SARS-CoV-2 Virus RNA by RT-qPCR at Specified Timepoints

Proportion of patients positive for SARS-CoV-2 virus RNA is defined as the proportion of patients with a positive qualitative virus RNA by RT-PCR test result, which will be analyzed at Day 3, Day 5, Day 7 and Day 14 separately. The statistical method is detailed in Section 5.1.

5.4.3.3 Area Under the Concentration Curve (AUC) in the Amount of SARS-CoV-2 Virus RNA as Measured by RT-qPCR

The statistical method is detailed in Section 5.1.

5.4.4 Supportive Secondary Safety Endpoints

5.4.4.1 Incidence of Adverse Events

Descriptive summaries of treatment-emergent adverse events will be presented.

5.4.4.2 Severity of Adverse Events

Descriptive summaries of treatment-emergent adverse events tabulated by severity will be presented.

5.4.4.3 Change from Baseline in Vital Signs

For each of the vital signs (pulse rate, respiratory rate, systolic and diastolic blood pressure, peripheral capillary oxygen saturation [SpO2], and temperature), descriptive statistics on absolute value and the change from baseline will be presented over time.

For vital signs, including oxygen saturation, time windows for unscheduled and early termination visits are given in Table 3 below. Where multiple measurements within a visit window are available for a patient, the value obtained closest to the target timepoint will be used.

Table 3 Vital Signs (including SpO2) Time Windows

Scheduled Timepoint	Acceptable Time Window
Baseline (Day 1 pre-dose)	Day 1 pre-dose
Day 3	Day 1 post-dose – Day 3
Day 5	Day 4 – Day 5
Day 7	Day 6 – Day 10
Day 14	Day 11 – Day 18

5.4.4.4 Change from Baseline in Targeted Laboratory Results

Laboratory data will use ranges from local laboratories and laboratory values will be converted to Système International units.

Summary tables will present the observed and change from baseline values of the laboratory chemistry parameters: alanine aminotransferase, aspartate aminotransferase, alkaline phosphatase, total bilirubin, blood urea nitrogen, creatine kinase, lactate dehydrogenase, C-reactive protein and creatinine, and laboratory hematology parameters: hemoglobin, white blood cell count, and platelets, and laboratory coagulation parameter: D-dimer for baseline and Day 5 visits by treatment group.

For laboratory results, time windows for unscheduled and early termination visits are given in [Table 4](#) below. Where multiple measurements within a visit window are available for a patient, the value obtained closest to the target timepoint (center of the acceptable time window) will be used.

Table 4 Laboratory Time Windows

Scheduled Timepoint	Acceptable Time Window
Baseline (Day 1 pre-dose)	Day 1 pre-dose
Day 5	Day 4 – Day 6

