Twenty subjects (10 subjects in the active group and 10 subjects in the placebo group) were enrolled and have completed dosing and follow-up through Day 10. No subjects have prematurely discontinued the study drug and no serious adverse events have been reported. All adverse events were mild, limited in duration, and were resolved by the end of the study.

There were no other clinically significant treatment-emergent laboratory abnormalities, ECG abnormalities, or vital sign abnormalities.

AT-03A-001

Phase II study AT-03A-001 is an ongoing randomized (1:1), double-blind, placebo-controlled study to evaluate the safety and efficacy of RO7496998 (AT-527) in adult patients with moderate COVID-19 who are at high risk for poor outcomes. Patients must have either obesity (BMI > 30), hypertension, diabetes, or asthma. The study protocol targets enrollment of 190 patients.

Patients are treated with RO7496998 (AT-527) at doses of 550 mg or matching placebo, BID (approximately every 12 hours) for 5 days (total of 10 doses).

Safety reviews have been performed by a Data Safety Monitoring Board (DSMB) for the first two 20-patient cohorts (40 patients total) with a data cutoff date of 11 December 2020. Data remains blinded in this ongoing study. To date, pertinent events reviewed by the DSMB include:

- Serious adverse events assessed by the investigator as unrelated to study drug were reported in 3 patients: 2 patients experienced decreased oxygen saturation (1 case resulting in death due to COVID-19 pneumonia) and 1 patient experienced acute respiratory failure. Progression of COVID-19 is common in this clinical setting.
- Grade 3 or 4 adverse events of laboratory abnormalities were reported in 2 patients: in 1 patient, one event each of isolated lipase increase and isolated triglycerides increase with no associated symptoms; and in another patient, one event of hyperbilirubinemia (normal ALT/AST).
- Grade 3 and 4 laboratory abnormalities of special interest for nucleosides did not reveal any signals or patterns suggestive of drug toxicity.

Cumulative blinded data review from 40 patients enrolled in the study continues to support a favorable safety profile of RO7496998 (AT-527). The study DSMB recommended the study continue without modification.

Refer to the AT-527 Investigator's Brochure for details on nonclinical and clinical studies.

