Some nucleoside analogs have been associated with mitochondrial toxicity, resulting in damage to the liver, muscles, heart, nerve, pancreas, and other organs. Nephrotoxicity has also been associated with the use of some nucleoside analogues (e.g., tenofovir), but this is not a broad class effect. The completed nonclinical assessments of RO7496998 (AT-527) indicate no potential for mitochondrial toxicity. The active triphosphate of RO7496998 (AT-527), AT-9010, did not inhibit the in vitro enzyme activities of human cellular DNA-dependent DNA polymerases (α , β , or γ) and was poorly incorporated by human mitochondrial RNA polymerase. Additionally, using cell-based assays, RO7496998 (AT-527) had no effect on mitochondrial cell membrane integrity, mitochondrial-dependent adenosine triphosphate production or mitochondrial biogenesis. To date, there have been no clinical signs of adverse effects suggesting mitochondrial toxicity for RO7496998 (AT-527) in animal toxicology studies or in completed clinical studies.

Current medically used nucleoside analogs are primarily metabolized in the kidney, and dose adjustments are generally not needed for patients with creatinine clearance values ≥ 60 mL/min. Therefore, this study excludes patients with creatinine clearance < 60 mL/min.

RO7496998 (AT-527) has not been associated with hepatotoxicity in nonclinical or clinical experience to date. A total of 82 subjects (30 healthy volunteers and 52 patients infected with HCV, including patients with cirrhosis), have received RO7496998 (AT-527) at various dose levels in completed clinical studies. In patients infected with HCV, liver function test values tend to normalize with RO7496998 (AT-527) treatment. No hepatotoxicity was observed in animal models (multiple species).

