4.5.5 Laboratory, Biomarker, and Other Biological Samples

Samples for the following laboratory tests will be sent to the study site's local laboratory for analysis. Collection of hematology, chemistry, coagulation and pregnancy laboratory samples will be performed locally as per schedule of activities. Historical standard-of-care laboratory tests performed locally, prior to obtaining written informed consent, may be used as the screening labs as indicated below; such tests do not need to be repeated for screening. If standard-of-care laboratory tests are conducted prior to obtaining written informed consent, documentation of results must be available.

Blood sample collection may be performed by a MN professional.

- Hematology: WBC count, RBC count, hemoglobin, hematocrit, platelet count, and differential count (neutrophils, eosinophils, basophils, monocytes, lymphocytes, other cells). If using a historical standard-of-care test, it must be performed \leq 48 hours prior to randomization.
- Chemistry panel (serum or plasma): bicarbonate or total carbon dioxide (if considered standard of care for the region), sodium, potassium, chloride, glucose, BUN or urea, creatinine, total protein, albumin, phosphate, calcium, total and direct bilirubin, ALP, ALT, AST, triglycerides, CK, CRP, ferritin, cholesterol, amylase, lipase, urate, procalcitonin, and LDH. If using a historical standard-of-care test, it must be performed \leq 48 hours prior to randomization.
- Pregnancy test

All women of childbearing potential will have a pregnancy test at screening. This will be a urine or serum test depending on local guidelines. If a historical serum test is conducted, it must be performed \leq 48 hours prior to randomization.

- SARS-CoV-2 approved diagnostic test (RT-PCR or validated rapid antigen test) for screening by an NP swab. If using a historical test, it must be performed \leq 72 hours prior to randomization.
- Coagulation: INR, aPTT, PT, D-dimer, and fibrinogen. If using a historical standard-of-care test, it must be performed \leq 48 hours prior to randomization.

Samples for the following laboratory tests will be sent to designated central laboratories or the Sponsor or a designee for analysis:

- Plasma samples for PK analysis
- Serum samples for SARS-CoV-2 antibody titer and virology tests
- NP or nasal swabs and saliva samples for SARS-CoV-2 virology tests
- NP or nasal swabs for respiratory pathogen co-infections panel (multiplex BioFire® assay)

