5.1.1 Risks Associated with RO7496998 (AT-527)

RO7496998 (AT-527), at once daily doses up to 553 mg (free base), has been evaluated in two clinical studies (AT-01B-001 and AT-01B-002) in healthy volunteers and patients infected with HCV. In the first study, 88 subjects were dosed with blinded study drug (RO7496998 [AT-527] or placebo), with 72 of the 88 subjects receiving active study drug. RO7496998 (AT-527) was well tolerated in both healthy volunteers and patients infected with HCV as either single or multiple doses (seven daily doses) up to 600 mg RO7496998 (AT-527) (equivalent to 553 mg AT-511 free base). In the second study, 10 patients infected with HCV received RO7496998 (AT-527) 550 mg in combination with 60 mg daclatasvir once daily for 8–12 weeks. There were no serious adverse events, dose-limiting toxicities, or premature discontinuations. RO7496998 (AT-527) is currently being evaluated in a Phase II study (AT-03A-001) at 550 mg BID in hospitalized patients with moderate COVID-19 and risk factors for poor outcomes. Safety data from the first 40 patients has not revealed any safety concerns (see Section 1.3). This dose has also been evaluated in healthy volunteers in the AT-03A-002 study, and has been well-tolerated, with no safety concerns (see Section 1.2).

To date, there have been no appreciable patterns of treatment-related or dose-related clinical adverse events or laboratory abnormalities from nonclinical or clinical studies.

Some nucleoside analogues have been associated with mitochondrial toxicity, resulting in damage to liver, muscles, heart, nerve, pancreas, and other organs. Nephrotoxicity has also been associated with the use of some nucleoside analogs (e.g., tenofovir), but is not a broad class effect. The completed nonclinical assessments of RO7496998 (AT-527) indicate no potential for mitochondrial toxicity. To date, there have been no clinical signs of adverse events suggesting mitochondrial toxicity for RO7496998 (AT-527) dosing.

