6.5 SAFETY ANALYSES

All safety analyses will be based on the safety analysis population, which will consist of all randomized patients who received at least one dose of study drug, with patients grouped according to treatment received. Safety analyses will include adult and adolescent patients. Additional safety analyses divided by age subgroup may also be produced and will be specified in the SAP.

Safety will be assessed through descriptive summaries of treatment emergent adverse events (nature, frequency, severity, and causality). Adverse events will be listed. All verbatim adverse event terms will be mapped to MedDRA thesaurus terms, and adverse event severity will be graded according to the NCI CTCAE v5.0 scale. Safety will be assessed through descriptive summaries of adverse events, vital sign measurements (including SpO₂), and laboratory test results (serum chemistry and hematology including complete blood count with differential and platelet counts).

A treatment-emergent adverse event is defined as any new adverse event reported or any worsening of an existing condition on or after the first dose of study drug.

Separate summaries will be generated for serious adverse events, deaths, adverse events leading to discontinuation of study drug, and adverse events of special interest.

Adverse events will be summarized by MedDRA term, appropriate thesaurus level, and toxicity grade.

Descriptive summaries of laboratory values at baseline and throughout the study will be tabulated by treatment arm. For selected parameters, changes from baseline and the proportion of patients experiencing clinically significant changes relative to baseline will be summarized by treatment arm.

Values, along with change from baseline, will be summarized using descriptive statistics for each vital sign parameter.

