5.6.3 Laboratory Data

Summaries of the number of patients by NCI CTCAE v5.0 grade for hematology (white blood cells [WBC], hemoglobin, platelets), and for chemistry (alkaline phosphatase, ALT,

AST, total bilirubin, creatinine), and renal function will be produced. The number of patients will be summarized by NCI CTCAE grade category for baseline and worst post baseline value.

Patients with values outside the reference will be listed, with an indication of the direction of the abnormality (high, low).

A listing of patients who meet the pre-specified criteria shown in [Table 5](#) during the study will be presented for each treatment group.

Table 5 Pre-specified Treatment-Emergent Abnormal Laboratory Criteria

AST (U/L) or ALT (U/L) and Total bilirubin (mg/dL)
AST (U/L) or ALT (U/L) $> 3 \times$ Baseline
AST (U/L) or ALT (U/L) $> 5 \times$ Baseline
AST (U/L) or ALT (U/L) $> 3 \times$ Baseline in combination with total bilirubin (mg/dL) $> 2 \cdot ULN$

ALT= alanine aminotransferase; AST= aspartate aminotransferase; ULN= upper limit of normal.

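### The SAP's laboratory lists leave lipase, amylase, triglycerides and neutrophils out of every by-arm laboratory summary, and CK out of the grade table, without declaring the narrowing

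*SAP*

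**What the plan says.** **What is collected.** Protocol 4.5.5 lists a chemistry panel that ends with "ALP, ALT, AST, triglycerides, CK, CRP, ferritin, cholesterol, amylase, lipase, urate, procalcitonin, and LDH". The hematology panel includes a differential count with neutrophils.

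**What the protocol promises.** Protocol 6.5 puts serum chemistry and hematology with a differential within the laboratory safety assessment and states: "Descriptive summaries of laboratory values at baseline and throughout the study will be tabulated by treatment arm". Its next sentence confines changes from baseline, and clinically significant changes, to selected parameters.

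**What the SAP specifies.** There are two by-arm laboratory summaries.
- SAP 5.4.4.4 gives observed values and change from baseline at baseline and Day 5 for ALT, AST, ALP, "total bilirubin, blood urea nitrogen, creatine kinase, lactate dehydrogenase, C-reactive protein and creatinine, and laboratory hematology parameters: hemoglobin, white blood cell count, and platelets", and D-dimer.
- SAP 5.6.3 gives "Summaries of the number of patients by NCI CTCAE v5.0 grade for hematology (white blood cells [WBC], hemoglobin, platelets), and for chemistry (alkaline phosphatase", continuing with ALT, AST, total bilirubin and creatinine, and adding renal function, at baseline and at the worst post-baseline value.

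SAP 5.6.3 also lists patients with out-of-range values and, through Table 5, patients who meet liver-test criteria. SAP Appendix 1 declares three changes to protocol-planned analyses: the population name, the hazard-ratio wording and the optional interim analysis. None concerns laboratory parameters.

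**What the protocol says about the risk.** Protocol 5.1.1 notes: "Some nucleoside analogues have been associated with mitochondrial toxicity, resulting in damage to liver, muscles, heart, nerve, pancreas, and other organs". The same section adds: "The completed nonclinical assessments of RO7496998 (AT-527) indicate no potential for mitochondrial toxicity". Protocol 1.2 reports Grade 3 or 4 laboratory adverse events in 2 of the first 40 patients of the blinded Phase II COVID-19 study: "in 1 patient, one event each of isolated lipase increase and isolated triglycerides increase with no associated symptoms", and hyperbilirubinemia in the other patient.

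**The concern.** The protocol collects pancreatic markers, CK and neutrophils and mentions pancreas and muscle when it describes the drug class. It also reports a lipase and a triglyceride increase from an earlier study. The SAP then names its laboratory parameters item by item and leaves most of these out. Bilirubin, the other analyte among those Phase II events, is in both by-arm summaries; lipase and triglycerides are in neither.

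At stake is the completeness of the descriptive safety comparison. Protocol 5.3.5.4 says that not every laboratory abnormality counts as an adverse event. An isolated rise without symptoms, intervention or change of treatment becomes one only if the investigator judges it clinically significant. For rises not judged so, a by-arm laboratory table is the place to compare the arms. For the omitted analytes the SAP text provides none.

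**Working it through.** No sample size, power or alpha figure is in question, so the check is a comparison of lists.

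**Step 1: the named analytes.**

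| Analyte | Collected (Protocol 4.5.5) | Observed and change by arm (SAP 5.4.4.4) | CTCAE grade (SAP 5.6.3) |
|---|---|---|---|
| Lipase | yes | no | no |
| Amylase | yes | no | no |
| Triglycerides | yes | no | no |
| Neutrophils | yes (differential) | no | no |
| CK | yes | yes | no |
| Total WBC | yes | yes | yes |
| Total bilirubin | yes | yes | yes |

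**Step 2: the whole panel.** Counting alternatives such as BUN or urea once, Protocol 4.5.5 collects 26 chemistry and 11 hematology items: 26 + 11 = 37. SAP 5.4.4.4 covers 9 chemistry and 3 hematology items: 9 + 3 = 12. (D-dimer belongs to coagulation and is outside this count.) The 8 individually named items in the grade table are all among those 12. So 37 − 12 = 25 items are in neither summary, and 12 − 8 = 4 have change from baseline but no grade table: BUN, CK, LDH and CRP.

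**Step 3: against the protocol's promise.** The word *selected* in Protocol 6.5 attaches to change from baseline and clinically significant change. The word *targeted* in the endpoint table attaches to change from baseline. Neither limits the general sentence on by-arm tabulation, and the differential is named in that section. No component of the differential appears in either SAP summary.

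**Step 4: what remains by arm.** SAP 5.1 tabulates treatment-emergent adverse events by system organ class and Preferred Term and presents descriptive summaries by treatment group. SAP 5.4.4.2 adds severity. A lipase rise reported as an adverse event is therefore counted by arm. CK has mean, SD, median, minimum and maximum by arm under SAP 5.1 and 5.4.4.4. The remainder is abnormalities of lipase, amylase, triglycerides and neutrophils, and graded CK elevations, that no investigator reported as an adverse event.

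**Step 5: could such a table be informative? (illustration with assumed rates)** Take all 1386 randomized patients at 2:1: 1386 × 2/3 = 924 active and 1386 / 3 = 462 placebo. For rates p0 (placebo) and p1 (active), with a two-sided 0.05 normal approximation,

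power = Φ[(|p1 − p0| − 1.96·SE0) / SE1],

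where SE0 uses the pooled rate and SE1 the separate rates. For 1% against 3%:
- pooled rate = (462 × 0.01 + 924 × 0.03) / 1386 = 0.0233
- SE0 = √[0.0233 × 0.9767 × (1/462 + 1/924)] = 0.00860
- SE1 = √[0.0099/462 + 0.0291/924] = 0.00727
- power = Φ[(0.02 − 0.01686) / 0.00727] = Φ(0.43) ≈ 67%

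The same formula gives about 26% for 1% against 2% and 92% for 1% against 4%. These rates are not in the documents. They show only that a trial of this size could reveal a moderate imbalance if the table existed.

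**The case against.** A reader might infer that pancreatic and muscle risk gets no arm comparison and that only a patient listing is left. The documents do not support that. The adverse event tables by Preferred Term and severity remain. The Phase II lipase and triglyceride increases were themselves recorded as adverse events in a patient without symptoms, so that route can work for isolated rises. CK has a by-arm summary that includes the maximum; only its grade table is missing.

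Other stronger readings also fail:
- Protocol 5.3.5.4 says not every abnormality is an adverse event. It does not say that asymptomatic rises often escape reporting, and clinically significant results must be reported.
- Neutrophils are not among the class risks named in Protocol 1.3 and 5.1.1, and total WBC is both summarized and graded. Their addition rests only on the promised differential.
- The protocol attributes mitochondrial toxicity to some analogues, says the nonclinical work on this drug indicates no such potential, and reports that Grade 3 and 4 abnormalities of special interest for nucleosides in the Phase II study showed no pattern suggestive of drug toxicity. The only laboratory-defined event of special interest is Hy's Law, which matches the liver-only Table 5.
- One patient in 40 is 2.5% (exact 95% CI 0.06% to 13.2%), and 1386 × 0.025 ≈ 35. That projection carries one blinded case from a hospitalized population into this trial and says nothing about a difference between arms. The point does not rest on it.

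Two further objections have some weight. The wording on targeted and selected parameters lets the SAP choose what goes into the change-from-baseline table, although it does not cover the general by-arm tabulation. And the SAP's introduction places table specifications in a separate document that is not available here, so the finding concerns the SAP text rather than the final outputs.

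**Conclusion.** The omission stands as a matter of text. Four collected analytes are in neither by-arm laboratory summary, CK is missing from the grade table, the SAP's scope is narrower than Protocol 6.5, and SAP Appendix 1 does not say so. If the lists are followed as written, the trial will have no by-arm rate of pancreatic-marker, graded CK or neutrophil abnormalities that were not recorded as adverse events.

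Severity is minor. The tables are descriptive, no hypothesis test or error rate is affected, and part of the information reaches the reader through the adverse event tables and the CK summary. The conclusion assumes that the SAP's parameter lists are complete and that the separate table specifications do not extend them.

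**What to change.** - **SAP 5.4.4.4:** add lipase, amylase, triglycerides and absolute neutrophil count to the observed and change-from-baseline tables by arm.
- **SAP 5.6.3:** add the same four and CK to the by-arm CTCAE v5.0 tables of baseline against worst post-baseline grade, for each parameter to which CTCAE grading applies.
- **SAP Appendix 1:** if any of the narrowing is kept, record it there with the reason, and align the separate table specifications.

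The cost is a short SAP edit and a few table rows. It needs no new samples or visits and no change to sample size or multiplicity control.

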4.3.2.1 RO7496998 (AT-527) and Placebo

RO7496998 (AT-527) is provided as 275 mg tablets; two tablets will be administered orally BID from Day 1 to Day 5. Matching placebo is provided as 275 mg tablets; two tablets will be administered orally BID from Day 1 to Day 5.

RO7496998 (AT-527) (or matching placebo) should be taken orally at 12-hour intervals (± 2 hours). If the first study dose is taken prior to 2:00 p.m. on Day 1, the next dose should be taken in the evening of the same day (i.e., prior to midnight on the same calendar day with a minimum of 10 hours between doses). For these patients, the final (tenth) dose will be taken in the evening of Day 5. However, if the first study dose is taken after 2:00 p.m. on Day 1, the next dose should be taken in the morning of Day 2. For these patients, the final (tenth) dose will be taken on the morning of Day 6.

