4.6.2 Patient Discontinuation from the Study

Patients who discontinue from study participation will return to the clinic for an early termination visit 7 (± 2) days after their final dose of study drug. Patients who discontinue from the study after Day 14 will not be required to complete an early termination visit.

Patients have the right to voluntarily withdraw from the study at any time for any reason. In addition, the investigator has the right to withdraw a patient from the study at any time.

Reasons for patient discontinuation from the study may include, but are not limited to, the following:

- Patient withdrawal of consent
- Study termination or site closure
- Adverse event
- Loss to follow-up
- Patient non-compliance, defined as failure to comply with protocol requirements as determined by the investigator or Sponsor

Every effort should be made to obtain a reason for patient discontinuation from the study. The primary reason for discontinuation from the study should be documented on the appropriate eCRF. If a patient requests to be withdrawn from the study, this request must be documented in the source documents and signed by the investigator.

Patients who withdraw from the study will not be replaced.

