Appendix 1: Schedule of Activities

Day	Screening	Treatment ^a					Monitoring					UV	ET ^{b, e} (±2 days)
	-2 to -1	1 ^b	2 ^b	3 ^b	4	5 ^b	7 ^{a, b}	14 ^{a, b}	21 (±2 days) (TC)	28 (±2 days) (TC)	33 ^{c, d} (+3 days) (TC)		
Nasopharyngeal swab using a SARS-CoV-2 approved diagnostic test (RT-PCR or validated rapid antigen test)	x ^r												
Nasopharyngeal swab ^s		x ^s		x		x	x	x				(x)	x
Saliva sample ^s		x ^s	x ^t	x		x	x	x				(x)	x
Plasma PK sample		Refer to Appendix 2 for PK sampling schedule.										(x)	
Serum sample for biomarkers and virology	x				x	x	x					(x)	x
Serum sample for biomarkers (optional intensive sampling group only) ^u	x		x		x	x	x					(x)	x
Blood sample for RNA analysis	x				x	x	x					(x)	x
Blood sample for RNA analysis (optional intensive sampling group only) ^u	x		x		x	x	x					(x)	x
Blood sample for cryopreserved PBMCs (optional intensive sampling group only) ^{u, v}	x				x	x	x						x
Nasosorption™ sample	x ^w				x ^w		x ^w					(x)	x ^w
Blood sample for WGS (optional) ^x	x												
RO7496998 (AT-527) administration ^y	x	x	x	x	x								
Concomitant medications ^z	←										→		
Adverse events ^{aa}	←										→		

BID = two times a day; COVID-19 = coronavirus disease 2019; ET = early termination; PBMC = peripheral blood mononuclear cell; PK = pharmacokinetic; PGIS = Patient Global Impression of Severity; QID = four times a day; RT-PCR = reverse-transcriptase polymerase chain reaction; SARS-CoV-2 = Severe Acute Respiratory Syndrome coronavirus-2; SpO₂ = peripheral capillary oxygen saturation; TC = telephone call; UV = unscheduled visit; WGS = whole genome sequencing.

Notes: On treatment Day 1, all assessments should be performed **prior to dosing** and on treatment Days 2–5, where possible all assessments should be performed prior to dosing, unless otherwise specified.

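### SAP Table 4's only post-baseline laboratory window (Day 4 to Day 6) almost never catches the early termination labs it is meant to place

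*SAP*

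**What the plan says.** **The summary and its window.** SAP 5.4.4.4 presents observed and change-from-baseline values for 13 targeted parameters "for baseline and Day 5 visits by treatment group". It then states: "For laboratory results, time windows for unscheduled and early termination visits are given in" Table 4. That table has a baseline row (Day 1 pre-dose) and one post-baseline row, Day 5, which accepts Day 4 to Day 6.

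**General rules.** SAP 5.1 uses time windows only where a section specifies them. Its paragraph on secondary safety endpoints says the reported data run to study completion or discontinuation and take in the ET visit where there is one. SAP Table 2 lists change from baseline in targeted laboratory results as a secondary safety endpoint.

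**The sister table.** SAP Table 3, for vital signs, is introduced in the same way. Its windows run without a gap from Day 1 post-dose to Day 18.

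**Visit timing.** Under Protocol 4.6.2, patients who leave the study return for an "early termination visit 7 (± 2) days after their final dose of study drug". The exception is: "Patients who discontinue from the study after Day 14 will not be required to complete an early termination visit". Protocol 4.3.2.1 fixes the latest planned dose, for patients who start after 2 p.m.: "the final (tenth) dose will be taken on the morning of Day 6".

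**When labs are drawn.** Protocol Appendix 1 schedules hematology, chemistry and coagulation at screening, at one on-treatment visit (Day 5 in the SAP), at unscheduled visits as needed, and at ET.

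**Other laboratory outputs.** SAP 5.6.3 tabulates CTCAE grade at baseline and at the worst post-baseline value, lists out-of-range results, and lists patients who meet the Table 5 liver criteria. It states no time window for any of these.

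**The concern.** Table 4 exists to say where ET and unscheduled results go. If its one post-baseline row closes before ET visits normally begin, the rule fails for one of the two visit types it names. ET labs are scheduled and collected, yet the summary has no place for them.

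The patients affected are those who leave the study before the Day 5 draw. Unless they have an unscheduled draw on Day 4 to Day 6, the ET sample is the only post-baseline laboratory result that could represent them. Protocol 4.6.2 lists adverse events among the reasons for leaving, so their absence may not be random. A by-arm summary without them leans toward patients who stayed.

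Some parameters have little cover elsewhere. CK is one example. Protocol 1.3 and 5.1.1 note that some nucleoside analogs have been associated with muscle damage, while also saying that the nonclinical work on this drug showed no potential for mitochondrial toxicity. CK is in the change-from-baseline summary but is not named in the grade tables.

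**Working it through.** The documents state no figure to reproduce here. The check compares visit days.

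**Inputs**
- Last-dose day d: 1 to 6 (Protocol 4.3.2.1).
- ET day: d + 7 ± 2, that is d + 5 to d + 9 (Protocol 4.6.2).
- Laboratory window: Day 4 to Day 6 (SAP Table 4).
- Vital sign windows: Day 1 post-dose to 3, 4 to 5, 6 to 10, 11 to 18 (SAP Table 3).

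**Step 1: place each on-schedule ET visit**

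| Last dose | Allowed ET days | Nominal ET day | ET days inside Day 4–6 | ET days inside Table 3 |
|---|---|---|---|---|
| Day 1 | 6–10 | 8 | Day 6 only | 5 of 5 |
| Day 2 | 7–11 | 9 | none | 5 of 5 |
| Day 3 | 8–12 | 10 | none | 5 of 5 |
| Day 4 | 9–13 | 11 | none | 5 of 5 |
| Day 5 | 10–14 | 12 | none | 5 of 5 |
| Day 6 | 11–15 | 13 | none | 5 of 5 |

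There are 6 × 5 = 30 combinations. Table 4 holds 1 and Table 3 holds 30. At the nominal 7 days, Table 4 holds 0 of 6.

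**Step 2: restrict to the patients who matter.** Patients whose last dose is on Day 5 or 6 have mostly passed the Day 5 draw already and keep that value. For a last dose on Day 1 to Day 4 there are 4 × 5 = 20 combinations, and again 1 fits. These are counts of possible timings. They are not probabilities, because nothing says the timings are equally likely.

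**Step 3: see what SAP 5.6.3 recovers.** The 13 parameters in SAP 5.4.4.4 divide as follows.
- Also in the worst post-baseline grade tables (8): ALT, AST, alkaline phosphatase, total bilirubin, creatinine, white cells, hemoglobin, platelets.
- Not named there or in Table 5 (13 − 8 = 5): CK, LDH, CRP, D-dimer and BUN. BUN may be covered, because SAP 5.6.3 also grades renal function without naming the analytes.

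Table 4 is invoked only in SAP 5.4.4.4, and SAP 5.1 applies windows only where specified. ET values for the first group therefore reach the grade tables. Late values for the second group reach only the out-of-range listing.

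**Step 4: test the fix.** A row for Day 7 to Day 18 holds the other 29 combinations. With the existing row, that makes 29 + 1 = 30 of 30.

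**The case against.** The strongest reply is that SAP 5.4.4.4 deliberately summarizes baseline and Day 5. A narrow window keeps values from Day 8 or later out of a Day 5 mean, and ET values are better judged in worst-grade tables, which already exist. Much of this stands. ET values should not be pooled with Day 5, and SAP 5.6.3 is a real backstop for eight parameters. Clinically significant abnormalities must also be reported as adverse events (Protocol 5.3.5.4). It does not explain why the sentence introducing Table 4 names ET visits, or why the vital sign table places them all.

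Two textual replies are weaker. The SAP 5.1 sentence on ET data sits in a paragraph mainly about adverse events, but the paragraph opens with secondary safety endpoints, and this is one of them. SAP Table 2 uses laboratory data up to study withdrawal, which might be read as excluding a later visit, but SAP 5.4.4.4 itself sets out to place ET results.

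A reader might infer more than the documents support:
- **That every post-treatment value is lost.** The Day 5 draw is usually before that day's dose ("on treatment Days 2–5, where possible all assessments should be performed prior to dosing"), which invites this reading. But patients who stop drug and stay in the study keep their scheduled assessments (Protocol 4.6.1), so their Day 5 value is post-treatment and counts. So does an unscheduled Day 6 value after a last dose on Day 5.
- **That all early leavers drop out.** Those who leave after the Day 5 draw keep that value.
- **That the window catches nothing.** It takes unscheduled labs on Day 4 to Day 6 and one edge case at ET.
- **That late values vanish from laboratory safety reporting.** SAP 5.6.3 shows otherwise.

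**Conclusion.** The point holds as a specification error in one descriptive secondary safety summary. Table 4 misses 29 of 30 on-schedule ET timings and every nominal one. This does not fit SAP 5.1 and is unlike Table 3. Patients who leave the study before the Day 5 draw normally have no post-baseline value in the change-from-baseline summary even when ET labs exist. For CK, LDH, CRP and D-dimer, and for BUN unless renal function covers it, such values are otherwise seen only in an out-of-range listing.

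The result assumes that ET visits are made on schedule; an ET visit made sooner than 5 days after the last dose could fall inside the window. It also assumes no unscheduled draw on Day 4 to Day 6.

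The number of patients affected cannot be computed. A reader might attach an assumed withdrawal rate to the 1386 planned patients, but the documents give no rate for leaving before Day 5 and none for attending ET, so any such count would be conjecture. The primary endpoint and the multiplicity plan are not affected.

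**What to change.** Add a separate row to SAP Table 4: Early termination / post-treatment, Day 7 to Day 18, ending where Table 3 ends. Extend the summary in SAP 5.4.4.4 to report observed and change-from-baseline values for this row by arm, with the number of patients contributing. Keep it apart from the Day 5 row so that the Day 5 means do not change. State that the row describes a selected group, made up of ET attenders and as-needed draws, and is descriptive only. If the existing nearest-to-centre rule is kept, the centre is (7 + 18) / 2 = Day 12.5, so a tie rule for Days 12 and 13 is needed.

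The change uses data already collected and needs only a SAP edit and one more table block, with no protocol amendment. The row recovers only leavers who attend ET or have a later unscheduled draw. An added laboratory panel, for example at Day 14, is not recommended: it would be an extra study procedure requiring a protocol amendment, and the correction does not depend on it.
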